4.3.4 Treatment of participants

All eligible participants will be treated with the respective treatment regimen according to their treatment arm assigned by randomisation at day 0. Ivermectin tablets (ODT and standard tablets) will be obtained from Liconsa, and an individual number of tablets according to bodyweight and dose will be administered. Albendazole will be the product of GSK (Zentel®) and a single tablet of 400 mg will be administered. Placebo tablets will be purchased from Zentiva Pharma GmbH, Germany.

The tablets will be handed out from four drug containers (placebo, ivermectin ODT, ivermectin standard tablets, and albendazole). According to the randomisation list, each person will receive either:

- (i) Placebo (number corresponding to 200 µg per kg bodyweight) plus a single tablet of albendazole
- (ii) 100 μg ivermectin ODT per kg bodyweight plus a single tablet of albendazole
- (iii) 200 µg ivermectin ODT per kg bodyweight plus a single tablet of albendazole

- (iv) 300 µg ivermectin ODT per kg bodyweight plus a single tablet of albendazole
- (v) 400 µg ivermectin ODT per kg bodyweight plus a single tablet of albendazole
- (vi) 200 µg ivermectin standard tablets per kg bodyweight plus a single tablet of albendazole

All drugs will be administered in the presence of the Principal Investigator (PI) and/or Co-PI, and ingestion confirmed. This will be recorded with the time and date of dosing. Participants will be asked to limit the use of any drugs other than those prescribed by the study medical team for the duration of the study as described in section 5.5. After ingestion of the medication, the participants will be observed for three hours to ensure retention of the drug. Vomiting within one hour post-dosing will require redosing. The participants will not be allowed more than one repeated dose. No re-administration will be needed for participants vomiting after one hour. The PI or the Co-PIs are responsible for drug accountability at the study site. Maintaining drug accountability includes careful and systematic study drug storage, handling, dispensing, and documentation of administration. Prior to administration, drugs will be stored at room temperature and protected from light and exposure to moisture in a secure area with limited access at the study site.

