4.3.6 Assessment of acceptability

To better understand the acceptability of ivermectin ODT compared to standard ivermectin tablets in PSAC, the palatability of each formulation (ODT and standard tablets crushed and swallowed with water) will be rated by children aged 4-5 years using a 100 mm VAS incorporating a 5-point pictorial hedonic scale (Figure 2) [33]. This rating will take place within 5 minutes after receiving the treatment. Additionally, participants will complete a short questionnaire directly after treatment administration and the interviewers will observe the participants during medication administration and record any discomfort or difficulties in taking the medication.

[figure not shown]

Figure 2. 100 mm hedonic visual analogue scale [33].

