4.4 Measure to minimise bias

Study participants eligible for treatment will be randomly assigned to one of the six treatment arms using a computer-generated stratified randomisation code. The random allocation sequence with a block size of 6 stratified by two levels of age category (24-47 months and 48-71 months) and two levels of baseline *T. trichiura* infection intensity (light: 1-999 EPG, and moderate or heavy: ≥1000 EPG) will be provided by a statistician. Allocation concealment will be warranted using opaque, sealed envelopes containing the randomisation lists. All treatment arms will be single-blinded (*i.e.* study participants will be blinded) using appearance and texture matching placebos. Only the study pharmacist administering the treatment will be aware of treatment allocation; all trial team members assessing the outcomes will remain uninformed. In the case of accidental unblinding or necessary code breaks, the sponsor will be immediately notified (within 24 hours) and data will be analysed as set forth in section 8.3.

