9.3 Project management

The trial team will include the PI ([name]), three Co-PIs ([name], [name], [name]), a study physician ([name] [name]), a study pharmacist ([name]), and a statistician ([name]), as well as a local medical team and several laboratory technicians. The PI and Co-PIs will be responsible for staff management, communication with the collaborative group, recruitment monitoring, data management, safety reporting, analysis, report writing and dissemination of the trial results. The Co-PIs are responsible for supervision of the lab and field technicians, staff management, participant recruitment and enrolment monitoring, supply of the material, contact to the local authorities and participating communities.

The study site (PHL-IdC) has more than 20 years of research experience with a special focus on neglected tropical diseases, including trichuriasis, and owns well-established diagnostic laboratories in parasitology and other infectious disease fields, run by trained and experienced technicians.

Infrastructure as required for the study needs will be installed as necessary before study launch. The investigator team is responsible for ensuring that the protocol is strictly followed. No changes should be made without the agreement of the PI and the Co-PIs, except when necessary to eliminate an apparent immediate hazard or danger to a study participant. All investigators will work according to the protocol and GCP. All investigators may take any steps judged necessary to protect the safety of the participants, whether specified in the protocol or not. Any such steps must be documented. During the treatment, the records are maintained by the responsible Co-PI. All entries have to be made clearly readable with a pen. All investigators must be thoroughly familiar with the properties, effects and safety of the investigational pharmaceutical product.

10. Ethical considerations

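### Section 4.4 promises that every outcome assessor is masked, but the dosing procedures let the attending PI or Co-PI and the acceptability interviewers recognise some arms

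*Combined protocol and SAP*

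**What the plan says.** Section 4.4 makes two statements. The first concerns participants: "All treatment arms will be single-blinded (*i.e.* study participants will be blinded) using appearance and texture matching placebos". The second is wider and concerns staff: "Only the study pharmacist administering the treatment will be aware of treatment allocation; all trial team members assessing the outcomes will remain uninformed".

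Other sections describe what happens at dosing and who does what afterwards:

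- Section 4.3.4 on attendance: "All drugs will be administered in the presence of the Principal Investigator (PI) and/or Co-PI, and ingestion confirmed".
- Section 4.3.4 on supply: "The tablets will be handed out from four drug containers", listed there as placebo, ODT, standard tablet and albendazole. On quantity, "an individual number of tablets according to bodyweight and dose will be administered". The placebo number follows the 200 µg/kg dose. No placebo top-up and no double-dummy is described.
- Sections 4.3.6 and 8.3 describe the standard tablets as crushed and taken with water.
- Section 4.3.6 on acceptability, a secondary endpoint: "the interviewers will observe the participants during medication administration and record any discomfort".
- Section 4.3.5 confines PK finger-pricks to 12 children in the ODT 200 µg/kg arm and 12 in the standard-tablet arm.
- Section 9.3 gives the PI and Co-PIs "recruitment monitoring, data management, safety reporting, analysis, report writing and dissemination of the trial results".
- Section 8.3 requires analysis sets to be settled ahead of unblinding.

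**The concern.** The trial claims only participant blinding, and an investigator who sees a dose does not breach that. The difficulty is the second sentence of Section 4.4, which tells the reader that allocation knowledge stops at the pharmacist and that no assessor has it. The acceptability interviewers are assessors and watch the tablets being taken. At least one of the PI and Co-PIs is in the room each time, and that group also holds decisions that depend on masking.

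The exposed items are those that need judgement:

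- acceptability as observed by the interviewers;
- any adverse-event (AE) or relatedness judgement made by someone who was at dosing;
- membership of the per-protocol set, for which Section 8.3 gives no criteria;
- discontinuation for non-compliance at PI or Co-PI discretion (Section 5.4);
- case-by-case handling of anthelminthic co-medication at analysis (Section 5.5).

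Safety by dose is one of the two stated grounds for choosing a dose (Section 3). Expectations about higher doses could colour AE judgements in exactly the comparison of interest.

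**Working it through.** **Plan's own figure.** Six arms of 35 (Sections 4.2 and 8.2): 6 × 35 = 210, as stated. The point does not depend on the sample-size calculation.

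**Step 1: who is where.**

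| Role | At dosing? | Later judgement |
|---|---|---|
| Pharmacist | Yes (4.4) | None stated |
| PI and/or a Co-PI | Yes, every dosing (4.3.4) | Safety reporting, analysis (9.3); discontinuation (5.4) |
| Acceptability interviewers | Yes (4.3.6) | Observed acceptability |
| Physician or nurse grading AEs | Not stated (6.1.1, 6.2) | Severity; Section 6.1.2 names no assessor for relatedness |
| Kato-Katz technicians | Nothing places them there (4.3.1, 4.3.8) | Primary endpoint |

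Rows 2 and 3 conflict with Section 4.4. Rows 4 and 5 do not, on the text given.

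**Step 2: what an observer can see.** Tablet count = weight (kg) × dose (µg/kg) ÷ 1000 ÷ tablet strength (mg), rounded. Before rounding, the four ODT doses stand at 1:2:3:4, and placebo equals the 200 µg/kg count.

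The documents give no tablet strength, weights or rounding rule. The figures below assume a single ODT strength, weights of 8 to 22 kg, a minimum of one tablet, and rounding either to nearest or up.

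| Assumed strength | Share of weights at which all four ODT counts differ |
|---|---|
| 0.25 or 0.5 mg | 100% |
| 1 mg | 94–100% |
| 1.5 mg | 63–77% |
| 3 mg | 0% |

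Example at 12 kg with 0.5 mg tablets: 1.2, 2.4, 3.6 and 4.8 mg ÷ 0.5 = 2.4, 4.8, 7.2 and 9.6. Rounded up, that is 3, 5, 8 and 10 tablets, with placebo at 5. At 12 kg with 3 mg tablets, rounding up gives 1, 1, 2 and 2, so neighbouring doses merge.

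**Step 3: recognisable share.**

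- Low end: the standard-tablet arm, by form. 35/210 = 16.7%.
- Low end with PK: a finger-pricked child who did not receive crushed tablets must be ODT 200. (35 + 12)/210 = 47/210 = 22.4%.
- High end: ODT 100, 300 and 400 by count plus standard tablets by form. 4 × 35 = 140; 140/210 = 66.7%.
- High end with PK: (140 + 12)/210 = 152/210 = 72.4%.
- Not separable by sight even then: 210 − 152 = 58 children (35 placebo and 23 unsampled ODT 200).

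The high end also needs the observer to know the child's weight. The figures with PK need someone who saw both dosing and sampling. Staff who see only the sampling can narrow a child to two arms. Table 1 puts sampling at 1, 2, 4, 6 and 24 h, around the 3 h and 24 h AE assessments.

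**The case against.** The strongest reply is that the trial is declared single-blind, that the primary endpoint is an egg count read by technicians, and that little is lost. Much of this stands:

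- Full-analysis-set exclusions are objective (no follow-up data, or negative at baseline), and AEs are analysed descriptively.
- Palatability is scored by the children themselves. A crushed tablet cannot be disguised as an ODT to someone watching it being taken.
- Section 9.3 lists one PI and three Co-PIs, and Section 4.3.4 needs only one of them present. A Co-PI who stays away from dosing can remain masked.

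A reader might infer several stronger things that the documents do not support:

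- *Unmasked investigators assess AEs.* Section 9.3 gives the PI and Co-PIs safety reporting. Grading belongs to a physician or nurse, whom nothing places at dosing.
- *Investigators who saw the dose judge causality of all serious events.* The sentence in Section 6.1.4 that names investigators concerns events after the study period.
- *The containers identify the drug to bystanders.* Section 4.3.4 lists their contents and says nothing about labels.
- *Two thirds of children are effectively unmasked.* That is near the top of a range resting on an unstated tablet strength.

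One limit remains on any remedy. AE data come from caregiver interviews, and a caregiver who saw the tablets could be influenced whoever asks the questions.

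**Conclusion.** The concern holds as an inconsistency in the stated masking. Section 4.4 claims a property that Sections 4.3.4 and 4.3.6 do not provide for the attending PI or Co-PI or for the acceptability interviewers. Between 17% and 67% of children are recognisable at dosing (22% to 72% with PK sampling). The low end assumes that standard tablets are crushed, or otherwise look different from ODTs, throughout that arm. The high end assumes one low-strength ODT and an observer who knows the weight. The synopsis describes the ODTs as mini-tablets, which makes a low strength plausible but does not establish it.

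A reader might infer that the cure-rate result is biased. The documents do not support that, because nothing shows the Kato-Katz readers seeing the dose. The remaining route to the efficacy analysis is discretionary: the per-protocol set, discontinuations and co-medication review. The documents do not say that those decisions are made by people absent from dosing. The change is worth making because it is cheap and readers will rely on the sentence as written.

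**What to change.** Reconcile Sections 4.3.4, 4.3.6, 4.4, 8.3 and 9.3, and replace the blanket sentence in 4.4 with a statement of who is masked for which outcome:

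1. Kato-Katz readers see participant IDs only.
2. AE interviews, grading and relatedness are done by existing medical staff who did not watch dosing and, where possible, did not attend PK sampling. Where this cannot be arranged, for example at 3 h, the assessment is reported as unmasked.
3. Per-protocol eligibility and decisions on anthelminthic co-medication are made from ID-only data. The person deciding neither attended dosing nor produced or held the allocation list, for example a Co-PI kept away from dosing. The statistician is not automatically suitable: Section 4.4 has a statistician supply the sequence, and Section 9.3 lists only one.
4. Interviewer-observed acceptability is reported as unmasked.

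The cost is protocol wording and less flexible staffing on dosing days. Section 9.3 names a single study physician, so complete separation could need extra staff; the unmasked label in item 2 avoids that. Tablets, doses and sample size do not change.

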4.5 Study duration and duration of participation

The trial will last three months. Baseline screening is scheduled to start two months prior to treatment and follow-up stool sample collection will take place at 14-21 days after treatment, lasting approximately two weeks. Thus, the maximum time for participation will be three months. Schedules of visits are summarised in Table 1.

Table 1. Schedule of study visits.

	Screening Day -60 to -1		Follow up Day 14 to 21							
		0h	_	1h	2h	3h	4h	6h	24h	
Informed consent	X		men							
Diagnosis (stool examination)	X		treat							X
Medical history		X	and							
Clinical examination		X	ation							
Haemoglobin measurement		X	omis							
PK (microsampling)			Randomisation and treatment	X	X		X	X	X	
Capturing AEs and SAEs						X			X	X

5. Selection of trial participants

5.1 Recruitment

The trial will be carried out in children aged 2-5 years in the Wete district, Pemba Island, Tanzania. The trial will be implemented as community-based study in communities with endemicity of *T. trichiura* infection above 20% identified during previous trials. Parents/caregivers of potential participants will be invited to participate in an information session. The research team will explain the purpose and procedures of the study, as well as potential benefits and risks of participation. Attendees will be encouraged to ask questions which will be discussed in an open setting.

Caregivers interested in having their child participate in the study will be invited to complete the informed consenting process by signing the informed consent form (ICF). Participants having a signed ICF will be assessed for eligibility during screening procedures.

5.2 Inclusion criteria

- 1. Aged between 2 and 5 years (24-71 months; confirmed by birth certificate or similar document).
- 2. Written informed consent signed by parents/caregivers.
- 3. Agree to comply with study procedures, including provision of two stool samples at the beginning (baseline) and at follow-up assessment 14-21 days after treatment.
- 4. At least two slides of the quadruplicate Kato-Katz thick smears positive for *T. trichiura*.
- 5. Willing to be examined by a study physician prior to treatment.

5.3 Exclusion criteria

- 1. Presence or signs of major systemic illness, e.g. fever (temporal body temperature $\geq 38^{\circ}$ C) or severe anaemia (Hb level <70 g/l according to WHO [34]) upon initial clinical assessment.
- 2. History of severe acute disease or unmanaged, severe chronic disease (*i.e.*, condition is not as therapeutically controlled as necessary).
- 3. Use of anthelminthic drugs during study period.
- 4. Known allergy to study medication (*i.e.* ivermectin, albendazole).
- 5. Being prescribed or taking concomitantly medication with known contraindication or drug interactions with the study medication.
- 6. Concurrent participation in other clinical trials.

5.4 Criteria for discontinuation of trial

A participant can be discontinued from the study for the following reasons:

- 1. Withdrawal from the study (this can happen anytime as participation is voluntary and there are no further obligations once a participant withdraws).
- 2. At the discretion of the PI or Co-PI, if the participant is not compliant to the requirements of the protocol.

Discontinued participants will not be replaced. If, for any reason, a participant is discontinued from the study before the end of treatment evaluations, the AE assessment will still be conducted. Data obtained

prior to the withdrawal will be included in the analysis to ensure the validity of the trial. Data of withdrawn participants are fully anonymised once analysis is complete.

5.5 Concomitant medication

All medications taken between one month before treatment and the follow-up assessment at 14-21 days post-treatment must be recorded with indication, dose regimen, date and time of administration.

Medication(s)/treatment(s) permitted during the trial:

- Analgesics and antipyretics are allowed to be given to participants in case of fever, antiemetics to prevent nausea and vomiting and/or antibiotics to prevent or treat bacterial superinfection.

Medication(s)/treatment(s) NOT permitted during the trial:

- No other active drugs against helminths are permitted during the trial. Participants receiving active anthelminthic concomitant medication during the trial will not be discontinued; however, a case-specific assessment will be done at the point of data analysis.

6. Safety assessments

6.1 Adverse event definitions

The term "adverse event" (AE) is defined as follows:

Any untoward medical occurrence in a patient or clinical investigation participant administered a pharmaceutical product and which does not necessarily have to have a causal relationship with this treatment.

An AE could therefore include any of the following events, which develop or increase in severity during the course of the study, after administration of the study product:

- a. Any unfavourable and unintended signs, symptoms or disease temporally associated with the use of a medicinal product, whether or not considered related to the condition under study and the study product.
- b. Any abnormality detected during physical examination.

The medical conditions present at the initial trial visit that do not worsen in severity or frequency during the trial will not be defined as AEs, but considered as baseline medical conditions. For the purpose of this trial, disease progression and relapse will be considered as failure of prescribed treatment or failure of treatment administration, not as an AE.

The observation time for AEs starts when the treatment is initiated until the end of the study.

These data will be recorded on the appropriate CRF sections, regardless of whether they are thought to be associated with the study or the drug under investigation. Associated with the use of the drug means

that there is a reasonable possibility that the event may have been caused by the drug (see also relatedness definitions below).

6.1.1 Severity grading

Adverse signs or symptoms will be graded by the physician or nurse of the trial as mild, moderate, severe or life threatening according to the following definitions:

Grade	Definition
1	Mild: the participant is aware of the event or symptom, but the event or symptom is easily tolerated.
2	Moderate : the participant experiences sufficient discomfort to interfere with or reduce his or her usual level of activity.
3	Severe : significant impairment of functioning: the participant is unable to carry out his or her usual activities.
4	Life-threatening or disabling
5	Death related to AEs

6.1.2 Relatedness

Relatedness will be assessed as defined below based on the temporal relationship between the AE and the treatment, known side effects of treatment, medical history, concomitant medication, course of the underlying disease and trial procedures.

Possibly related: an AE, which can medically (pharmacologically/clinically) be attributed to the study treatment.

Unrelated: an AE, which is not reasonably related to the study treatment. A reasonable alternative explanation must be available.

An AE that is determined to be related to the administration of a study product is referred to as an "adverse drug reaction".

6.1.3 Expectedness

Expected adverse drug reaction: Any AE possibly related to the administration of ivermectin, albendazole or ivermectin-albendazole combination reported in the literature or on the drug package leaflets, if available, and listed in the consent form.

Unexpected adverse drug reaction: Any AE possibly related to the study drug administration, the nature, frequency, specificity or severity of which is unanticipated and not consistent with the available risk information described for these drugs.

6.1.4 Serious adverse events

According to the ICH "Clinical Safety Data Management: Definitions and standards for expedited Reporting E2A" [35], a serious adverse event (SAE) includes any event (experience) or reaction in any untoward medical occurrence that at any dose:

- 1. results in death;
- 2. is life-threatening, meaning, the participant was, in the view of the Investigator, at immediate risk of death from the reaction as it occurred, *i.e.* it does not include a reaction that, had it occurred in a more serious form, might have caused death;
- 3. results in persistent or significant disability/incapacity, *i.e.* the event causes a substantial disruption of a person's ability to conduct normal life functions;
- 4. requires inpatient hospitalization or prolongation of existing hospitalization;
- 5. creates a congenital anomaly or birth defect (not relevant for this study);
- 6. is an important medical event, based upon appropriate medical judgement, that may jeopardize the participant or may require medical or surgical intervention to prevent one of the other outcomes defining serious.

A "severe" AE does not necessarily meet the criteria for a "serious" AE. SAEs are reported from treatment until the end of the study.

SAEs that are still ongoing at the end of the study period will be followed up to determine the final outcome.

The causality of any SAE that occurs after the study period and its possible relatedness to the study treatment or study participation will also be assessed by investigators as described in section 6.1.2.

